10.6.1 Hypoglycemia

During the study, patients are instructed to document the presence or absence of hypoglycemic episodes or hypoglycemic symptoms in their study diary. The hypoglycemia will be reported in the specific eCRF page with onset date and time, symptoms and/or signs, the SMBG value if available, and the treatment. If the event fulfills SAE criteria, hypoglycemia will also be reported as an SAE.

Hypoglycemia is categorized according to the American Diabetes Association workgroup on hypoglycemia classification (21) and summarized in [Figure 1](#).

In addition to the threshold of ≤ 3.9 mmol/L (≤ 70 mg/dL), hypoglycemia episodes with a plasma glucose of < 3.0 mmol/L (< 54 mg/dL) will be analyzed separately.

Figure 1 - Hypoglycemia classification in Study EFC14868

*The patient is not able to treat her/himself because of the acute neurological impairment and requires another person to actively administer sugar, glucagon or intravenous glucose

PG = plasma glucose; SAE = serious adverse event

Severe hypoglycemia

Severe hypoglycemia is an event requiring assistance of another person to actively administer carbohydrate (sugar), glucagon, intravenous glucose, or other resuscitative actions. These episodes may be associated with sufficient neuroglycopenia to induce seizure, unconsciousness, or coma. Self-monitored plasma glucose values may not be available, but neurological recovery attributable to the restoration of plasma glucose to normal is considered sufficient evidence that the event was induced by a low plasma glucose concentration.

Note: “Requiring assistance of another person” means that the patient could not help himself or herself to treat the hypoglycemia. Assisting a patient out of kindness, when assistance is not required, should not be considered a “requires assistance” incident.

Any hypoglycemic event which leads to unconsciousness, coma, or seizure should also be reported as an **SAE**.

Documented symptomatic hypoglycemia

Documented symptomatic hypoglycemia is an event during which typical symptoms of hypoglycemia accompanied by a measured plasma glucose concentration of ≤ 3.9 mmol/L (≤ 70 mg/dL).

Clinical symptoms that are considered to result from a hypoglycemic episode include increased sweating, nervousness, asthenia/weakness, tremor, dizziness, increased appetite, palpitations, headache, sleep disorder, confusion, seizures, unconsciousness, or coma.

Asymptomatic hypoglycemia

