2.1.4.1 Hypoglycemia

Hypoglycemia will be identified as events recorded on the dedicated e-CRF “Hypoglycemic event information” page, and will be categorized as follows (see study protocol for further details):

Severe hypoglycemia

Severe hypoglycemia is an event requiring assistance of another person to actively administer carbohydrate, glucagon, intravenous glucose or other resuscitative actions. These episodes may be associated with sufficient neuroglycopenia to induce seizure, unconsciousness or coma.

Self-monitored plasma glucose values may not be available, but neurological recovery attributable to the restoration of plasma glucose to normal is considered sufficient evidence that the event was induced by a low plasma glucose concentration.

Severe hypoglycemia is identified in e-CRF “Hypoglycemic event” page as those documented as, To the question “Countermeasure Administration”, ticked the option “Subject was Not Capable of Treating Self and Required Assistance”, and

To the question “Were Symptoms Present”, ticked “Yes”.

Documented symptomatic hypoglycemia

Documented symptomatic hypoglycemia is an event during which typical symptoms of hypoglycemia accompanied by a measured plasma glucose concentration of ≤ 3.9 mmol/L (≤ 70 mg/dL).

Clinical symptoms that are considered to result from a hypoglycemic episode are eg, increased sweating, nervousness, asthenia/weakness, tremor, dizziness, increased appetite, palpitations, headache, sleep disorder, confusion, seizures, unconsciousness, or coma.

Documented symptomatic hypoglycemia is identified in e-CRF “Hypoglycemic event” page as those documented as,

- To the question “Countermeasure Administration”, NOT ticked the option “Subject was Not Capable of Treating Self and Required Assistance”, and
- To the question “Were Symptoms Present”, ticked “Yes”, and
- With a plasma glucose value before countermeasure ≤ 3.9 mmol/L (≤ 70 mg/dL).

Asymptomatic hypoglycemia

Asymptomatic hypoglycemia is an event not accompanied by typical symptoms of hypoglycemia but with a measured plasma glucose concentration ≤ 3.9 mmol/L (≤ 70 mg/dL).

Asymptomatic hypoglycemia is identified in e-CRF “Hypoglycemic event” page as those documented as,

- To the question “Countermeasure Administration”, NOT ticked the option “Subject was Not Capable of Treating Self and Required Assistance”, and
- To the question “Were Symptoms Present”, ticked “No”, and

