2.4.5.1 Analyses of hypoglycemia

Analyses of hypoglycemia will be performed on the TEAE period as defined in [Section 2.1.4](#). For the purpose of hypoglycemia analyses during the 18-week randomized core treatment period, the TEAE period for 18-week randomized core treatment period is (1) the time from the first administration of the double-blind IMP up to 1 day after the last administration of IMP if the patient discontinued treatment on or before Visit 12 (or Day 126 if Visit 18 date is missing), or (2) the time from the first administration of the double-blind IMP to the administration at Visit 12/Week 18 (or Day 126 if Visit 12/Week 18 date is missing) if the patient remained treated beyond Visit 12/Week 18. Hypoglycemia will be classified as severe hypoglycemia, documented symptomatic hypoglycemia, asymptomatic hypoglycemia, probable symptomatic hypoglycemia or relative hypoglycemia (see [Section 2.1.4.1](#)).

The number (%) of patients with any hypoglycemia, severe hypoglycemia and documented symptomatic hypoglycemia will be summarized respectively by treatment group during the TEAE period, as well as the incidence rate in patient years. Two types of incidence rates will be presented: the number of patients with at least 1 event per 100 patient-years (calculated as the number of patients with at least 1 event / total exposure in 100 patient-years), and the number of events per 100 patient-years (calculated as the total number of events / total exposure in 100 patient-years). Note: here exposure (in days) is the duration of TEAE period, ie, duration of IMP treatment in days +1 (see [Section 2.1.4](#)).

The summary of frequency and incidence rate in patient years for severe hypoglycemia or documented symptomatic hypoglycemia will be provided as appropriate by gender (Male, Female), age group (<50, ≥50 to <65, ≥65 years), race (White, Black or African American, Asian, Other), sulfonylurea use at Week -1 (yes, no).

The number (%) of patients with at least 1 severe hypoglycemia or documented symptomatic hypoglycemia during the TEAE period, as well as the corresponding number of events, will be summarized as necessary by hour of the day for each treatment group, using the following hour intervals: ≥23:00 to <06:00, ≥06:00 to <10:00, ≥10:00 to <14:00, ≥14:00 to <18:00, ≥18:00 to <23:00.

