2.5.3 Missing data

For categorical variables, patients with missing data are not included in calculations of percentages unless otherwise specified. When relevant, the number of patients with missing data is presented.

Derived variables will be considered missing if any of the original variables required to calculate them are missing. For example, if either a baseline assessment or an endpoint assessment is missing for a particular patient, then change from baseline at endpoint will be missing. Depending upon the assessment, analyses may not include all patients in the analysis population, because certain patients in the intended population may have missing data.

Incomplete date of first administration of double-blind IMP

Date/time of first administration is the first non-missing start date/time of double-blind IMP completed in the e-CRF “First dose IMP” module.

For patients who are randomized and dispensed a double-blind treatment kit but who are lost to follow-up just after Visit 6 (eg. only the treatment kit number is reported in the e-CRF “Exposure

- treatment period” module without any dose information), the date of first administration will be imputed using the date of randomization. When a patient is randomized but not exposed, “Not taken” should be ticked in the e-CRF “First dose IMP” module.

Handling of computation of treatment duration if IMP end of treatment date is missing

For the calculation of the treatment duration, the date of the last dose of double-blind IMP is equal to the date of last administration reported on the e-CRF “Treatment status library” page. If this date is missing, the exposure duration should be left as missing.

The last dose administration should be clearly identified in the case report form and should not be approximated by the last returned package date.

Handling of medication missing/partial dates

No imputation of medication start/end dates or times will be performed. If a medication date or time is missing or partially missing and it cannot be determined whether it was taken prior or concomitantly, it will be considered a prior, concomitant, and post-treatment medication.

Handling of adverse events/hypoglycemia with missing or partial date/time of onset

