If the severity/grade is missing for 1 of the treatment-emergent occurrences of an adverse event, the maximal severity on the remaining occurrences will be considered. If the severity is missing for all the occurrences, a “missing” category will be added in the summary table.

Handling of potentially clinically significant abnormalities

If a patient has a missing baseline he will be grouped in the category “normal/missing at baseline.”

For PCSAs with 2 conditions, one based on a change from baseline value or a normal range and the other on a threshold value, with the first condition being missing, the PCSA will be based only on the second condition.

For a PCSA defined on a threshold and/or a normal range, this PCSA will be derived using this threshold if the normal range is missing; eg, for eosinophils the PCSA is > 0.5 GIGA/L or $>ULN$ if $ULN \geq 0.5$ GIGA/L. When ULN is missing, the value 0.5 should be used.

Measurements flagged as invalid by the laboratory will not be summarized or taken into account in the computation of PCSA values.

Linked adverse events that worsened or became serious

An AE that worsened or became serious will have a separate record in the data from the original event record with an AE identification number that links the new record to the original record. An AE that worsened or became serious will be considered a new recurring AE in the summary of recurrent events or in the summary of events by time intervals.

Handling of missing data for continuous efficacy endpoints

Please see [Section 2.4.4.1](#) and [Section 2.4.4.2](#).

Handling of missing data for categorical secondary efficacy endpoints

Please see [Section 2.4.4.2](#).

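### SAP 2.1.4.1: an assisted hypoglycemia event recorded without symptoms 'Yes' meets no category and leaves the severe count; reconcile the definition with the e-CRF rule and show such events separately

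*SAP*

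**What the plan says.** Protocol 10.6.1 gives the definition: "Severe hypoglycemia is an event requiring assistance of another person to actively administer carbohydrate (sugar), glucagon, intravenous glucose, or other resuscitative actions". SAP 2.1.4.1 opens its severe category with nearly the same sentence, and the titration notes in Protocol 8.2.1.3 also describe severe hypoglycemia as an event needing help from others. None of these prose statements names symptoms as a condition.

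SAP 2.1.4.1 then says how the category is found on the hypoglycemic event page. The assistance option must be ticked, and so must the symptom answer: "To the question “Were Symptoms Present”, ticked “Yes". Each of the other four categories carries the opposite assistance condition: "NOT ticked the option “Subject was Not Capable of Treating Self and Required Assistance".

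SAP 2.4.5.1 expects every event to be placed: "Hypoglycemia will be classified as severe hypoglycemia, documented symptomatic hypoglycemia, asymptomatic hypoglycemia, probable symptomatic hypoglycemia or relative hypoglycemia". Table 3 of SAP 2.1.4.2 lists severe hypoglycemia among the events of special interest that are not adjudicated and identifies it by this same algorithm. SAP 2.4.5.2 reports it through the hypoglycemia summary.

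No rule addresses a blank symptom answer specifically. The nearest text is the general convention in SAP 2.5.3: "Derived variables will be considered missing if any of the original variables required to calculate them are missing".

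**The concern.** The stated definition has one element and the programmed rule has two. Where an investigator ticks that the patient could not self-treat and needed help, but answers 'No' to symptoms or leaves that answer blank, the event meets the prose definition and fails the rule. It cannot fall into a neighbouring category either, because all four are closed to assistance-ticked events.

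The result is odd at one point. With symptoms 'No' and glucose at or below 70 mg/dL, an event without the assistance tick is asymptomatic hypoglycemia. Adding the tick, which signals a worse event, removes it from every category.

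At stake are the severe counts and rates, the severe-or-documented summaries by subgroup and hour of day, the Kaplan-Meier curve for time to first such event, and the special-interest count. No committee reviews severe hypoglycemia, so adjudication would not recover an event that the algorithm misses. The trial adds study drug to basal insulin and stratifies on sulfonylurea use, so readers will look at this table.

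**Working it through.** The plan gives no figure on this point, so the check is one of form logic followed by the weight of a single event.

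**1. Which entries reach a category.** The five rules of SAP 2.1.4.1 were applied to every combination of assistance (ticked, not ticked), symptoms (Yes, No, blank), glucose before countermeasure (at or below 70, above 70, none) and prompt recovery (Yes, No): 2 × 3 × 3 × 2 = 36 combinations, 18 of them with assistance ticked.

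- Assistance ticked, symptoms Yes: 6 of 6 are severe.
- Assistance ticked, symptoms No: 0 of 6 meet any category.
- Assistance ticked, symptoms blank: 0 of 6 meet any category.

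Glucose and recovery play no part in the severe rule, so these counts say only that the symptom answer decides everything. They are not frequencies. A blank fails the Yes condition whether or not the general rule in SAP 2.5.3 is applied. That rule is illustrated by change from baseline, and extending it to event classification is an inference.

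**2. Where the event remains visible.** SAP 2.1.4.1 identifies hypoglycemia as events on the dedicated page, and SAP 2.4.5.1 tabulates any hypoglycemia, so the event can still count there. SAP 2.4.5.1 also lists every event on that page. SAP 2.1.4.1 records it as an SAE if it meets SAE criteria or led to unconsciousness, coma or seizure.

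**3. What one event is worth.** Planned arm sizes are 280, 140 and 140 (Protocol 11.1). Assume that all randomized patients are treated for the full period. Exposure follows SAP 2.4.5.1: treatment days plus 1, so 364 + 1 = 365 days over 52 weeks, and 126 days for the 18-week period in patients who continue beyond it.

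- Proportion: 1/140 = 0.71%; 1/280 = 0.36%.
- 52 weeks, n = 140: 140 × 365/365.25 = 139.9 patient-years; 100/139.9 = 0.71 events per 100 patient-years.
- 52 weeks, n = 280: 279.8 patient-years; 0.36.
- 18 weeks, n = 140: 140 × 126/365.25 = 48.3 patient-years; 2.07.
- 18 weeks, n = 280: 96.6 patient-years; 1.04.

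If mean exposure were 80% of planned (an assumption; the documents give no figure), the patient-years become 111.9, 223.8, 38.6 and 77.3, and the rate shifts 0.89, 0.45, 2.59 and 1.29. Any single event would carry this weight. How many events are affected cannot be derived.

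**The case against.** The best defence is that the symptom condition was meant. The footnote to Figure 1 in Protocol 10.6.1 attributes the inability to self-treat to acute neurological impairment. Such impairment is symptomatic, and the protocol's own symptom list includes "sleep disorder, confusion, seizures, unconsciousness, or coma". On this reading the symptom answer puts that element into practice, and an assisted event with truly no symptoms is not severe. The figure itself is not visible in the text available, so this cannot be settled. The defence stands as far as intent goes, and it means that a correctly completed form should say 'Yes'. It does not say what happens to an inconsistent or blank entry.

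The condition may also screen out mis-ticks. The protocol warns about one kind: "Assisting a patient out of kindness, when assistance is not required, should not be considered". That is fair, but an unclassified entry is a poor substitute for a query, and Protocol 13.4 already provides a query process. Whether the form has an edit check for this combination cannot be seen.

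Finally, the five rules are not exhaustive elsewhere. Without the assistance tick, symptoms 'Yes' with no glucose value and no prompt recovery meets no category, and neither does symptoms 'No' with glucose above 70 mg/dL. So unclassified entries are a general feature of the scheme. This one differs because the event satisfies the prose definition of the most serious category.

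**Conclusion.** The mismatch between prose and rule is real, and handling of assistance-ticked events without symptoms 'Yes' is not specified beyond the general missing-data convention. It is a minor point and a cheap improvement. It affects only entries that survive data queries, possibly none. Each would move a 140-patient arm by 0.71 percentage points under the full-treatment assumption.

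Several stronger readings are not supported:

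- A reader might infer that the symptom condition is simply an error and that assistance alone must define the category. The Figure 1 footnote leaves intent open.
- A reader might infer that severe hypoglycemia will be undercounted. Against the prose definition the rule can only lower the count, but against the footnote's reading an excluded event may be rightly excluded.
- A reader might infer bias between arms. The rule is the same in all arms and the safety tables are descriptive.
- A reader might infer that the event vanishes from the report. It can appear under any hypoglycemia, in the listing, and as an SAE where criteria are met.
- A reader might infer that a worst-case convention for missing safety data is breached. SAP 2.5.3 has no uniform one. For adverse event severity it says "If the severity is missing for all the occurrences, a “missing” category will be added in the summary table".

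**What to change.** In SAP 2.1.4.1, reconcile the definition with the e-CRF rule and say whether symptoms are part of the category. State how an assistance-ticked event with symptoms 'No' or blank is handled.

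Before unblinding, list every assistance-ticked event whose symptom answer is not 'Yes' and query it through the process in Protocol 13.4. Show any that remain unresolved as a separate row by arm in the hypoglycemia table, and give the severe count and the special-interest count with and without them. This does not require deciding that unresolved entries are severe.

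The cost is a short SAP clarification, one query listing, one extra row and the paired counts, with no new data collection. The downside is that a mis-ticked assistance box, for example symptoms 'No' with glucose above 70 mg/dL, could enter the inclusive count. The separate row makes that visible.

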2.1.4.2 Adverse events variables

Adverse event observation period

- Pretreatment adverse events are adverse events that developed or worsened or became serious from the signed informed consent date up to first administration of double-blind IMP
- Treatment-emergent adverse events are adverse events that developed or worsened or became serious during the treatment-emergent adverse event period
- Posttreatment adverse events are adverse events that developed or worsened or became serious during the posttreatment period.

All adverse events (including SAE, AESI and EOSI) will be coded to a lower-level term (LLT), preferred term (PT), high-level term (HLT), high-level group term (HLGT), and associated primary system organ class (SOC) using the version of MedDRA currently in effect at Covance at the time of database lock.

The occurrence of adverse events (including SAE, AESI and EOSI) will be recorded from the time of signed informed consent until the end of the study (see [Section 2.1.4](#)) or the resolution/stabilization of all SAE, AESI and EOSI.

AE SI include:

- Pregnancy
- Symptomatic overdose with IMP/NIMP
- Alanine aminotransferase (ALT) increase > 3 times upper limit of normal (ULN)

EO SI include:

- MACE (CV death, myocardial infarction, or stroke) and other specific cardiovascular events (eg, heart failure requiring hospitalization)
- Severe hypoglycemia
- Genital mycotic infections (to include vulvovaginal candidiasis in females and candida balanitis in males)
- Urinary tract infection
- Clinically relevant volume depletion and events related/possibly related to volume depletion
- Diarrhea
- Pancreatitis
- Bone fractures
- Venous thrombotic events, to include deep venous thrombosis and thromboembolism (to include pulmonary embolism)
- Diabetic ketoacidosis
- Renal events, to include 50% decline in eGFR, end stage kidney disease, renal death
- Malignancies of special interest (breast, bladder, renal cell, Leydig cell, pancreatic, prostate, and thyroid carcinoma)
- Adverse event leading to an amputation

A Clinical Endpoint Committee(s) (CEC) will in a blinded manner review and adjudicate all deaths, myocardial infarction, stroke, unstable angina requiring hospitalization, and heart failure requiring hospitalization, selected renal events, bone fracture, and diabetic ketoacidosis.

Two independent committees will review safety events that require ongoing monitoring to ensure timing protocol amendments in case a safety signal is identified. These events are: 1) potential cases of drug-induced liver injury (DILI), and 2) cases of amputations. The two committees will review the cases in a treatment-blinded manner and will present their assessment to the DMC.

AE SI and EO SI will be identified based on criteria in [Table 3](#).

Table 3 - Criteria for AESI and EOSI

AE Grouping	Criteria
AESI	
Pregnancy	eCRF "Pregnancy"
Symptomatic overdose with IMP/NIMP	"Overdose of IMP" or "Overdose of NIMP" checked and "Symptomatic overdose" checked in eCRF "Overdose"
ALT increase > 3X ULN	eCRF "ALT increase"
EOSI adjudicated	
Cardiovascular death	Positively adjudicated by CEC: "Cardiovascular" or "Undetermined" as the primary cause of death
Myocardial infarction, Unstable Angina requiring hospitalization	Positively adjudicated by CEC: Yes to the question "Does the event meet the definition of an MI for this study?", or Yes to the question "If event is not an MI, does the event meet the definition of an UA Requiring admission to hospital or emergency room, for this study?"
Stroke	Positively adjudicated by CEC: Yes to the question "Does the event meet the definition of a Stroke for this study?"
Heart failure requiring hospitalization	Positively adjudicated by CEC: Yes to the question "Does the event meet the definition of a Heart Failure Event for this study?"
Bone fractures	Positively adjudicated by CEC: Yes to the question "Did the Fracture occur?"
Diabetic ketoacidosis	Positively adjudicated by CEC: Yes to the question "Does this event meet the criteria to be a DKA event?"
EOSI Renal events where select events adjudicated	
Sustained $\geq 50\%$ decrease in eGFR	(1) For $\geq 50\%$ decrease in eGFR from baseline, (1a) confirmed $\geq 50\%$ decrease in GFR for ≥ 30 days with no reversible cause as recorded in eCRF "eGFR decrease", OR (1b) positively adjudicated by CEC: Yes to the question "Does the subject meet the criteria of CKD progression" for $\geq 50\%$ decrease in eGFR.
Sustained eGFR < 15 mL/min/1.73 m ²	(2) For eGFR < 15 mL/min/1.73 m ² , (2a) confirmed eGFR < 15 mL/min/1.73 m ² for ≥ 30 days with no reversible cause as recorded in eCRF form "eGFR decrease", OR (2b) positively adjudicated by CEC: Yes to the question "Does the subject meet the criteria of CKD progression".

Statistical Analysis Plan

Version: Final 2.0
Lexicon Pharmaceuticals Protocol No. EFC14868

Date of Issue: 04 December 2019
Covance Study ID:000000155200

AE Grouping	Criteria
Chronic dialysis	(3) For dialysis, (3a) dialysis lasted for ≥90 days (e.g. end date – start date+ 1 ≥90) as recorded in eCRF “Renal Event – Dialysis”, OR (3b) positively adjudicated by CEC: Yes to the question “. Does the subject meet the criteria for ESRD”.
Renal transplant *	(4) “Renal transplant” captured in eCRF “Other procedure form”, where adjudication is not required. PTs of Renal transplant (10038533), Renal and pancreas transplant (10052278), Renal and liver transplant (10052279) based on MedDRA v22.0.
Renal death	(5) Renal death as positively adjudicated by CEC: “Death - Non-Cardiovascular (Renal)” as the primary cause of death

EOSI not adjudicated *

Severe hypoglycemia	algorithm specified in Section 2.1.4.1 based on eCRF “Hypoglycemic Events”
Genital mycotic infections	PTs in Appendix B
Urinary tract infections	PTs in Appendix B
Clinically relevant volume depletion and events related/possibly related to volume depletion	PTs in Appendix B
Diarrhea	Narrow search on “Noninfectious diarrhoea (SMQ)” [20000218] plus the following PTs (MedDRA v22.0): Gastroenteritis (10017888), Antidiarrhoeal supportive care (10055660), Enteritis (10014866), Enteritis leukopenic (10014877), Enterocolitis (10014893), Enterocolitis haemorrhagic (10014896)
Pancreatitis	PTs in Appendix B
Venous thrombotic events	PTs in Appendix B

AE Grouping	Criteria
Malignancies of special interest	
Breast cancer: Narrow search on “Breast cancer: Narrow search on “Breast neoplasms, malignant and unspecified (SMQ)” [20000149]
 
Prostate cancer: Narrow search on “Prostate neoplasms, malignant and unspecified (SMQ)” [20000152]
 
Leydig-cell cancer: PTs of Leydig cell tumour of the testis (10024407) and Ovarian Sertoli-Leydig cell tumour (10073270) based on MedDRA v22.0
 
Thyroid cancer: PTs in Appendix B
 
Renal cell cancer: PTs in Appendix B
 
Pancreatic cancer: PTs in Appendix B
 
Bladder cancer: PTs in Appendix B

EOSI AE leading to an amputation

AE leading to an amputation	“AE Correction” as the reason for amputation in eCRF “Other Procedures related to Amputation”
AE potentially leading to an amputation *	PTs in Appendix B

* Search terms will be updated using the MedDRA version currently in effect at Covance at the time of database lock for EOSI identified by them.

* AE potentially leading to amputation: not belong to the EOSI list defined in protocol, the item is included and analyzed due to their relevance in regards to lower limb complications and amputations as a requirement from health authorities.

